6 SELECTION AND WITHDRAWAL OF SUBJECTS

6.1 Inclusion criteria

To be eligible to participate in this study, all of the following criteria must be met:

1. An Institutional Review Board (IRB)/Independent Ethics Committee (IEC) approved written Informed Consent Form (ICF) is signed and dated by the subject or by the legal representative.
2. Subject/legal representative is considered reliable and capable of adhering to the protocol (eg, able to understand and complete diaries), visit schedule, and medication intake according to the judgment of the Investigator.
3. Adult subjects (18 to 70 years of age, inclusive) must have a diagnosis of HS for at least 1 year prior to Baseline.
4. Hidradenitis suppurativa lesions must be present in at least 2 distinct anatomic areas, 1 of which must be at least Hurley Stage II or Hurley Stage III.
5. Subject must have stable HS for at least 2 months prior to Screening and also at the Baseline Visit as assessed by the Investigator through subject interview and review of medical history.
6. Subject must have had an inadequate response to at least a 3-month study of an oral antibiotic for treatment of HS (or exhibited recurrence after discontinuation to, or demonstrated intolerance to, or have a contraindication to oral antibiotics for treatment of their HS) as assessed by the Investigator through subject interview and review of medical history.
7. Subject must have a total abscess and inflammatory nodule count ≥ 3 at the Baseline Visit.
8. Subject must be considered, in the opinion of the Investigator, to be a suitable candidate for treatment with adalimumab per regional labeling.
9. Subject must have a C-reactive protein (CRP) level $>3\text{mg/L}$ at the Baseline Visit.
10. Subject has a negative tuberculosis (TB) Screening assessment (including an interferon-gamma release assay [IGRA] test using QuantiFERON-TB Gold test, or equivalent) and negative posterior-anterior chest x-ray (CXR) or Computed Axial

Tomography (CAT) scan of chest at Screening or within 3 months prior to Screening (nuclear magnetic resonance films are not acceptable).

11. Subject must agree to daily use (and throughout the entirety of the study) of 1 of the following over-the-counter topical antiseptics on their HS lesions: chlorhexidine gluconate, triclosan, benzoyl peroxide, or dilute bleach in bathwater.
12. Subject is assessed to have no other medical condition that would preclude their participation in the study, as determined by the Principal Investigator based upon the results of a medical history, physical examination, laboratory profile, and a 12-lead ECG performed during the Screening Period, and confirmed at Baseline.
13. **Female** subjects must be postmenopausal (at least 1 year; to be confirmed hormonally as part of the Screening process, if less than 2 years since last menstrual period), permanently sterilized (eg, tubal occlusion, hysterectomy, bilateral salpingectomy) or, if of childbearing potential, must be willing to use a highly effective method of contraception up till 20 weeks after last administration of IMP, and have a negative pregnancy test at Visit 1 (Screening) and immediately prior to first dose. The following methods are considered highly effective when used consistently and correctly.
 - combined (estrogen and progestogen) hormonal contraception associated with inhibition of ovulation (oral, intravaginal, or transdermal).
 - progestogen-only hormonal contraception associated with inhibition of ovulation (oral, injectable, implantable).
 - intrauterine device (IUD).
 - intrauterine hormone-releasing system (IUS).
 - bilateral tubal occlusion.
 - vasectomized partner (where postvasectomy testing had demonstrated sperm clearance).
 - sexual abstinence if it is in accordance with a subject's preferred and common lifestyle. Subjects who use abstinence as a form of birth control must agree to abstain from heterosexual intercourse until 20 weeks after the last dose of IMP. Study personnel must confirm the continued use of abstinence is still in accordance with the subject's lifestyle at regular intervals during the study.

Male subjects with a partner of childbearing potential must be willing to use a condom when sexually active, up till 20 weeks after the last administration of IMP (anticipated 5 half-lives).

6.2 Exclusion criteria

Subjects are not permitted to enroll in the study if any of the following criteria is met:

1. Prior treatment with anti-IL17s or participation in an anti-IL17 study.
2. Subjects who previously received anti-TNFs.
3. Subjects participating in another study of a medication or a medical device under investigation within the last 3 months or at least 5 half-lives of the investigational product,

whichever is greater, or is currently participating in another study of a medication or medical device under investigation.

4. Subject has a known hypersensitivity to any excipient(s) of bimekizumab or adalimumab.
5. Subject is using concomitant oral analgesics for HS-related or non-HS-related pain at study entry:
 - Opioid analgesics within 14 days prior to the Baseline Visit.
 - Non-opioid oral analgesics *unless* at a stable dose for at least 14 days prior to the Baseline Visit (PRN use is not considered a stable dose).
6. Subject requires, or is expected to require, opioid analgesics for any reason (excluding tramadol).
7. Subject received prescription topical therapies for the treatment of HS within 14 days prior to the Baseline Visit.
8. Subject received systemic non-biologic therapies for HS with potential therapeutic impact for HS less than 28 days prior to Baseline Visit.
9. Subject has a draining fistula count >20 at the Baseline Visit.
10. Subjects with a diagnosis of inflammatory conditions other than HS, including but not limited to PSO, PsA, RA, sarcoidosis, or systemic lupus erythematosus. Subjects with a diagnosis of CD or ulcerative colitis are allowed as long as they have no active symptomatic disease at Screening or Baseline.
11. Subjects with a history of chronic or recurrent infections, or a serious or life-threatening infection within the 6 months prior to the Baseline Visit (including herpes zoster). Subjects with a high risk of infection in the investigator's opinion (eg, subjects with leg ulcers, indwelling urinary catheter, persistent or recurrent chest infections, prior prosthetic joint infection at any time, subjects who are permanently bedridden or wheelchair assisted).
12. Subject has any current sign or symptom that may indicate an active infection (except for common cold), or has had an infection requiring systemic antibiotics within 2 weeks of the Baseline Visit.
13. Any other active skin disease or condition (eg, bacterial, fungal or viral infection) that may interfere with assessment of HS.
14. Subject has history of or current clinically active infection with Histoplasma, Coccidioides, Paracoccidioides, Pneumocystis, nontuberculous mycobacteria (NTMB), Blastomyces, or Aspergillus or current active Candidiasis (local or systemic).
15. Subject has acute or chronic viral hepatitis B virus (HBV), hepatitis C virus (HCV), or human immunodeficiency virus (HIV) infection. Subjects who have evidence of, or tested positive for, hepatitis B or hepatitis C are excluded.
 - A positive test for the HBV is defined as: 1) positive for hepatitis B surface antigen; or, 2) positive for anti-hepatitis B core antibody.

-
- A positive test for the HCV is defined as: 1) positive for hepatitis C antibody, and 2) positive via a confirmatory test for HCV (for example, HCV polymerase chain reaction).
16. Subjects with known TB infection, at high risk of acquiring TB infection, with latent TB infection (LTB), or current or history of NTMB infection (refer to [Section 11.3.1](#) for details on determining full TB exclusion criteria).
 17. Subject has a primary immunosuppressive condition, including taking immunosuppressive therapy following an organ transplant, or has had a splenectomy.
 18. Subjects with concurrent malignancy or history of malignancy (including surgically resected uterine/cervical carcinoma-in-situ) during the past 5 years will be excluded, with the following exceptions that may be included:
 - a. ≤ 3 excised or ablated, basal cell carcinomas of the skin.
 - b. One squamous cell carcinoma of the skin (stage T1 maximum) successfully excised, or ablated only (other treatments, ie, chemotherapy, do not apply), with no signs of recurrence or metastases for more than 2 years prior to Screening.
 - c. Actinic keratosis(-es).
 - d. Squamous cell carcinoma-in-situ of the skin successfully excised, or ablated, more than 6 months prior to Screening).
 19. Subject has a history of a lymphoproliferative disorder including lymphoma or current signs and symptoms suggestive of lymphoproliferative disease.
 20. Subject has history of demyelinating disease (including myelitis) or neurologic symptoms suggestive of demyelinating disease.
 21. Subjects with a current or recent history, as determined by the Investigator, of severe, progressive, and/or uncontrolled renal, hepatic, hematological, endocrine, pulmonary, cardiac (eg, congestive heart failure, New York Heart Association Grade 3 and 4), gastrointestinal (note: subjects with active peptic ulcer disease are excluded; subjects with a history of peptic ulcer disease are allowed), neurological disease, or inflammatory bowel disease.
 22. Subject has a history of uncompensated heart failure, fluid overload, or myocardial infarction, or evidence of new onset ischemic heart disease or (in the opinion of the Investigator) other serious cardiac disease, within 12 weeks prior to the Baseline Visit.
 23. Presence of active suicidal ideation, or positive suicide behavior using the “Baseline” version of the Columbia-Suicide Severity Rating Scale (C-SSRS) and the HADS with either of the following criteria:
 - Subject has a lifetime history of suicide attempt (including an actual attempt, interrupted attempt, or aborted attempt), or has suicidal ideation in the past 6 months as indicated by a positive response (“Yes”) to either question 4 or question 5 of the “Screening/Baseline” version of the C-SSRS at Screening.
 - HADS-D score ≥ 10 and HADS-A score ≥ 15 .

24. Subject has >2x upper limit of normal (ULN) of any of the following: alanine aminotransferase (ALT), aspartate aminotransferase (AST), *alkaline phosphatase (ALP), or >ULN total bilirubin ($\geq 1.5 \times \text{ULN}$ total bilirubin if known Gilbert's syndrome). If subject has elevations only in total bilirubin that are >ULN and <1.5xULN, fractionate bilirubin to identify possible undiagnosed Gilbert's syndrome (ie, direct bilirubin <35%).

*An isolated elevation between 2xULN and <3xULN of ALP is acceptable in the absence of an identified exclusionary medical condition.

Tests that result in ALT, AST, or ALP up to 25% above the exclusion limit may be repeated once for confirmation during the Screening Period. Upon retesting, subjects whose ALT, AST, or ALP remain above the thresholds defined above, should not be randomized.

For randomized subjects with a Baseline result >ULN for ALT, AST, ALP, or total bilirubin, a Baseline diagnosis and/or the cause of any clinically meaningful elevation must be understood and recorded in the electronic Case Report form (eCRF).

If subject has >ULN ALT, AST, or ALP that does not meet the exclusion limit at Screening, repeat the tests, if possible, prior to dosing to ensure there is no further ongoing clinically relevant increase. In case of a clinically relevant increase, inclusion of the subject must be discussed with the Medical Monitor and/or UCB Study Physician.

25. Subjects with clinically significant laboratory abnormalities (eg, creatinine >1.5xULN, neutropenia <1.5x10⁹/L, hemoglobin <8.5g/dL, lymphocytes <1.0x10⁹/L, platelets <100x10⁹/L). Individual Screening tests for which the results are in error, borderline, or indeterminate for inclusion in the study, can be repeated once for confirmation during the Screening Period if they are within 25% of the exclusion limit. Upon retesting, subjects whose results remain outside this threshold should not be randomized.
26. Subject has 12-lead ECG with changes considered to be clinically significant upon medical review (eg, QTc using Fridericia's correction [QTcF] >450ms, bundle branch block, evidence of myocardial ischemia).
27. Subject has received any live (includes attenuated) vaccination within the 8 weeks prior to the Baseline Visit (eg, inactivated influenza and pneumococcal vaccines are allowed but nasal influenza vaccination is not permitted). Live vaccines are not allowed during the study or for 20 weeks after the last dose of IMP.
28. Subject has received Bacillus Calmette-Guerin vaccination within 1 year prior to IMP administration.
29. Subject has a history of chronic alcohol or drug abuse within the previous 6 months.
30. Subjects with any other condition which, in the Investigator's judgement, would make the subject unsuitable for inclusion in the study.
31. Subject has previous exposure to adalimumab.
32. Subjects are Investigator site personnel directly affiliated with this study and/or their immediate families. Immediate family is defined as a spouse, parent, child, or sibling, whether biological or legally adopted.

33. Subjects are UCB employees or are employees of third-party organizations involved in the study.

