6.3 Withdrawal criteria

Subjects are free to withdraw from the study at any time, without prejudice to their continued care.

Subjects should be withdrawn from the study and encouraged to come for the SFU Visit (20 weeks after the last dose of IMP) if any of the following events occur:

1. Subject withdraws his/her consent.
2. The Sponsor or a regulatory agency requests withdrawal of the subject.

Subjects should be withdrawn from all IMP and will be asked to return for the study assessments 12 weeks after the first dose (ie, the Week 12 Visit) and for the SFU Visit (20 weeks after the last dose of IMP) if any of the following events occur:

1. There is confirmation of a pregnancy during the study, as evidenced by a positive pregnancy test.
2. Subject develops an illness that would interfere with his/her continued participation.
3. Subject considered to have either a suspected new LTBI infection or who develops active TB or NTM infection during the study (including but not limited to conversion demonstrated by IGRA or other diagnostic means) must be immediately discontinued from IMP and an Early Withdrawal Visit must be conducted as soon as possible, but not later than the next regular visit.

Confirmed active TB is an SAE and must be captured on an SAE Report Form and provided to the Sponsor in accordance with SAE reporting requirements. As with all SAEs, periodic follow-up reports should be completed as per protocol requirements until such time as the TB infection resolves.

Additional information on TB policies are provided in [Section 11.3.1](#).

4. Subject is noncompliant with the study procedures or medications in the opinion of the Investigator.
5. Subject uses prohibited concomitant medications, with the exception of topicals, as defined in this protocol ([Section 7.8.2](#)), that may present a risk to the safety of the subject in the opinion of the Investigator and/or the Medical Monitor and/or UCB Study Physician.
6. Subject develops total bilirubin $>2 \times \text{ULN}$ (except Gilbert's); neutropenia $<1.0 \times 10^9/\text{L}$; lymphopenia $<0.5 \times 10^9/\text{L}$.
7. Subject has active suicidal ideation as indicated by a positive response ("Yes") to questions 4 or 5 or to the suicidal behavior questions of the "Since Last Visit" version of the self-rated C-SSRS. The subject should be referred immediately to a Mental Healthcare Professional and must be withdrawn from the study.

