8. Subjects with a HADS-D score ≥ 15 must be withdrawn. Any subject who has a HADS-D score of ≥ 10 should be referred immediately to a Mental Healthcare Professional for further evaluation and potential withdrawal by the Investigator.

9. Subject experiences an AE as described below:
- Any Common Terminology Criteria for Adverse Events (CTCAE) Grade 3 and above AE that is assessed as related to study drug in the opinion of the Investigator.
 - If the event is deemed to be not related to study drug by the Investigator, the subject may remain in the study after approval by the Medical Monitor and/or UCB Study Physician.
 - Any CTCAE Grade 2 event that is evaluated as related to study drug in the opinion of the Investigator, is persistent, and falls into any of the following System Organ Classes: “Blood and lymphatic disorders,” “Cardiac disorders,” or “Vascular disorders.”
 - Persistent is defined as lasting 28 days or more, which spans at least 2 bimekizumab dosing visits.

10. Subject has a clinical laboratory value meeting the following criteria:

- CTCAE Grade 3 and above: subject must be withdrawn regardless of relationship to study drug or duration of event, unless the abnormal laboratory value is a natural variation of a condition pre-existing before Baseline (eg, hypercholesterolemia).
- CTCAE Grade 2
 - Subject may remain in the study if the event is transient. If a subject has a Grade 2 laboratory abnormality that is not an expected natural variation of a condition present before Baseline, a retest is required within 1 to 2 weeks at a scheduled or unscheduled visit. If the repeat value is below Grade 2, the subject may receive the next scheduled study treatment. If the value on the repeat is still Grade 2 or above, a second repeat test must be performed and results made available prior to the next scheduled study treatment. If this second repeat value is still Grade 2 or above, the subject must be withdrawn.

11. Subjects with newly diagnosed Inflammatory Bowel Disease (IBD) or with IBD flares during the study must:

- Be referred, as appropriate, to a healthcare professional treating IBD, such as a gastroenterologist
- Discontinue the IMP and be followed-up until resolution of active IBD symptoms

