8.2 Baseline Visit (Visit 2; Day 1)

The following procedures or assessments will be performed/recorded prior to administration of IMP:

- Confirm inclusion/exclusion criteria
- Contact the IRT for randomization
- Ensure no significant changes in medical history and concomitant disease
- Physical examination
- Body weight
- Concomitant medications
- Vital signs (BP, pulse rate, and temperature)
- Record 12-lead ECG
- C-SSRS
- TB questionnaire
- Photography and thermography (for subjects participating in the substudy)
- PGA of Skin Pain
- HS-Physician's Global Assessment
- DLQI
- EQ5D
- HADS
- Lesion count (including Hurley Stage); note that data collected from the lesion count will be used for the derivation of the HiSCR and IHS4
- Modified Sartorius score
- Erythema assessment
- Obtain blood sample(s) for:
 - Standard safety laboratory tests (hematology and biochemistry)
 - Bimekizumab plasma concentration
 - PD and nonhereditary pharmacogenomic variables
 - Pharmacogenetic variables (for subjects participating in the substudy)

-
- Anti-bimekizumab antibodies
 - Obtain urine sample for:
 - Standard safety laboratory tests
 - Urine pregnancy test for women of childbearing potential
 - Biomarker research
 - Obtain skin biopsy samples for:
 - lesional and nonlesional skin biopsy
 - Record AEs
 - IMP administration (after all other visit assessments completed)

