9.11 Hospital Anxiety and Depression Scale

The HADS was chosen for its well-established psychometric properties and its use in clinical research on biological therapy in subjects with other inflammatory skin diseases (Dauden et al, 2009; Langley et al, 2010). The HADS scores for anxiety and for depression range from 0 to 21 with higher scores indicating worse state. A score below 8 is considered to be normal whereas a score of 15 and above is considered severe (Snaith and Zigmond, 1994). A score of 11 to 14 is considered moderate.

10 ASSESSMENT OF PHARMACOKINETICS PHARMACODYNAMIC, NONHEREDITARY PHARMACOGENOMICS, AND PHARMACOGENETICS

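### Exclusion 23 does not bar entry with HADS-D ≥15 when HADS-A is <15, although withdrawal criterion 8 stops IMP on HADS-D ≥15 alone

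*Protocol*

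**What the plan says.** **Entry.** Protocol 6.2, exclusion 23 covers suicidality and HADS together. Its lead-in names suicidal ideation or behavior on the C-SSRS "and the HADS with either of the following criteria". The first bullet concerns suicide attempts and C-SSRS questions 4 and 5. The second is the only HADS threshold among the eligibility criteria: "HADS-D score ≥ 10 and HADS-A score ≥ 15".

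**Stopping.** Protocol 6.3, criterion 8 states: "Subjects with a HADS-D score ≥ 15 must be withdrawn". It adds that anyone with HADS-D of 10 or more "should be referred immediately to a Mental Healthcare Professional for further evaluation and potential withdrawal by the Investigator". The criterion stands in the list introduced by "Subjects should be withdrawn from all IMP and will be asked to return for the study assessments 12 weeks after the first dose", so it means stopping IMP, with the Week 12 and Safety Follow-Up Visits still requested. It has no HADS-A condition and no requirement of a change from Baseline.

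**Measurement.** Under Protocol 9.11, "The HADS scores for anxiety and for depression range from 0 to 21", and a score of 15 or more counts as severe. HADS is collected at Screening, at Baseline before dosing, and at Week 2 before that visit's IMP (Table 5–1; 8.1 to 8.3).

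**The concern.** A stopping limit and an entry limit on the same scale should fit together: nobody should be able to enter already beyond the value that obliges the site to stop treatment. Here the entry rule is a conjunction and the stopping rule is not, so the two diverge for subjects with severe depression scores and HADS-A below 15.

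What is at stake is safety and consistency. Depression is an adverse event for special monitoring, assessed with the HADS (Protocol 11.1.1.4). As written, the plan can expose a subject with a severe depression score to a loading dose and then require withdrawal two weeks later for a score known before dosing.

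**Working it through.** No sample size, power or error-rate figure is involved, so there is no plan figure to reproduce. The check is a comparison of the rules plus simple counts.

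**1. The two rules on the same score grid.** Each subscale takes the 22 values 0 to 21 (Protocol 9.11).

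- Pairs meeting the stopping rule (HADS-D 15–21, any HADS-A): 7 × 22 = 154.
- Of these, removed by exclusion 23 (HADS-A 15–21; the HADS-D ≥10 part is met automatically): 7 × 7 = 49.
- Of these, not removed (HADS-A 0–14): 7 × 15 = 105.

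The gap is exactly HADS-D 15–21 with HADS-A 0–14. These are score combinations, not patients; they locate the gap and say nothing about how often it occurs.

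**2. Other stopping limits, side by side (Protocol 6.2 and 6.3).**

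| Measure | Entry excludes | IMP stops |
|---|---|---|
| Total bilirubin | >ULN (Gilbert's allowance) | >2×ULN (except Gilbert's) |
| Neutrophils | <1.5×10⁹/L | <1.0×10⁹/L |
| Lymphocytes | <1.0×10⁹/L | <0.5×10⁹/L |
| C-SSRS questions 4 or 5 | positive | positive |
| HADS-D | ≥10, only if HADS-A ≥15 | ≥15 |

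The first four have an entry limit equal to or stricter than the stopping limit. HADS-D does not, which suggests a drafting gap.

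**3. Does criterion 8 apply only to new or worsened scores?** Elsewhere in 6.3 such limits are written out: criterion 6 applies when a subject develops an abnormality, and criterion 10 exempts natural variation in conditions that pre-date Baseline. Criterion 8 has neither qualifier. An unchanged score of 15 or more at Week 2 therefore meets it.

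**4. Exposure before the Week 2 stop, per affected subject (Protocol 7.2, Table 7–1; SAP 11.1).**

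- Injections: 4 + 5 × 2 + 3 × 1 = 17 planned; 4/17 = 24% given at Baseline.
- Bimekizumab: 640 + 5 × 320 = 2240mg planned; 640/2240 = 29%.
- Adalimumab: 160 + 80 + 7 × 40 = 520mg planned; 160/520 = 31%.

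**5. After the fix.** If HADS-D ≥15 excludes on its own, 0 of the 154 pairs pass entry.

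**The case against.** **Criterion 8 may already act at Screening.** Protocol 16.1 treats a person as enrolled once consent is signed, and HADS is measured at Screening, at least two weeks before randomization. A site could apply criterion 8 then, with nobody randomized and no dose given. This reading is possible and would close the gap. It is not secure: the list containing criterion 8 speaks of withdrawal from IMP and of a visit timed from the first dose, which fits dosed subjects better.

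**Other safeguards exist.** Inclusion 12, exclusion 30 and the mental-status part of the physical examination (11.3.5) let an investigator refuse such a subject, and criterion 8 itself calls for referral at HADS-D ≥10. All act on a score known before dosing, so the harmful path needs several things to go wrong together. But the refusal routes are discretionary, and none of these safeguards sets an entry threshold.

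**Stronger inferences that the documents do not support.**

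- *That the primary result is affected.* IMP withdrawal alone does not make a subject a non-responder: the Week 12 Visit is still requested, and SAP 4.2.1 imputes non-response for missing HiSCR or study discontinuation. An entry score also precedes randomization, so it creates no systematic difference between arms.
- *That analysis sets lose subjects.* A randomized but undosed subject would fall outside the SS, FAS and PPS (SAP 3.5.3 to 3.5.5). That happens only if criterion 8 is applied to the Baseline HADS after randomization and before dosing, which the text does not say.
- *That entry depression will trigger DMC referral.* Protocol 6.4.1 does name criterion 8, but introduces the trigger as a pattern of AEs. An unchanged entry score may not be an AE under 11.1.1.1.
- *That the Baseline Visit list puts randomization before HADS.* In 8.2, "Contact the IRT for randomization" is item 2 and HADS is item 16, under the lead-in "The following procedures or assessments will be performed/recorded prior to administration of IMP". The list cannot be chronological: the lesion count with Hurley Stage is item 17, yet Hurley Stage must be given to the IRT to randomize (7.10). Confirming eligibility is item 1.

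**The fix leaves a margin.** A subject entering at HADS-D 14 would still have to stop after a one-point rise. That is true, but it is worsening after entry, which a stopping rule is meant to catch.

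**Conclusion.** The mismatch is certain on the text: HADS-D ≥15 with HADS-A <15 meets no stated HADS exclusion and is at or above the mandatory IMP-withdrawal limit. The practical path, in which a subject is randomized, given 4 of 17 injections and stopped at Week 2, assumes that the investigator does not use discretion, that criterion 8 is not applied at Screening, and that the score is still 15 or more at Week 2.

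The number of subjects affected cannot be estimated and may be 0 of 80. Reading 105 of 154 as a share of patients would be wrong. The point is a cheap safety and consistency repair; it does not call the efficacy analysis into question.

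The lead-in to exclusion 23 adds a related ambiguity. It can be read as requiring C-SSRS suicidality as well as the HADS scores, which would narrow the HADS exclusion further and widen the gap.

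**What to change.** Reword the second bullet of exclusion 23 so that a subject is excluded if HADS-D is ≥10 together with HADS-A ≥15, or if HADS-D is ≥15 regardless of HADS-A, at Screening or at Baseline before randomization. In the same edit, change the lead-in so that this bullet clearly excludes on its own, without suicidality on the C-SSRS.

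No separate ordering instruction is needed in 8.2, because the bullet itself would require the score before randomization. No new assessment is needed either. The cost is one amended criterion and possibly a few more screen failures, a number that the documents do not allow to be estimated.
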